#### 4.3 Exclusion Criteria

Patients who meet any of the following exclusion criteria will **not** be eligible for this study:

- Is currently participating and receiving study therapy or has participated in a study of an investigational agent and received study therapy or used an investigational device within 4 weeks of the first dose of treatment.
- Has a diagnosis of immunodeficiency or is receiving systemic steroid therapy or any other form of immunosuppressive therapy within 7 days prior to the first dose of trial treatment.
- Has a known history of active TB (Bacillus Tuberculosis).
- Hypersensitivity to pembrolizumab or any of its excipients.
- Has had a prior anti-cancer monoclonal antibody (mAb) within 4 weeks prior to study Day 1 or who has not recovered (i.e.,  $\leq$  Grade 1 or at baseline) from adverse events due to agents administered more than 4 weeks earlier.
- Has had prior chemotherapy, targeted small molecule therapy, or radiation therapy within 2 weeks prior to study Day 1 or have not recovered (i.e.,  $\leq$  Grade 1 or at baseline) from adverse events due to a previously administered agent.
  - Note: Subjects with  $\leq$  Grade 2 neuropathy are an exception to this criterion and may qualify for the study.
  - Note: If subject received major surgery, they must have recovered adequately from the toxicity and/or complications from the intervention prior to starting therapy.
- Has a known additional malignancy that is progressing or requires active treatment. Exceptions include basal cell carcinoma of the skin or squamous cell carcinoma of the skin that has undergone potentially curative therapy or in situ cervical cancer.
- Has known active central nervous system (CNS) metastases and/or carcinomatous meningitis. Subjects with previously treated brain metastases may participate provided they are stable (without evidence of progression by imaging for at least four weeks prior to the first dose of trial treatment and any neurologic symptoms have returned to baseline), have no evidence of new or enlarging brain metastases, and are not using steroids for at least 7 days prior to trial treatment. This exception does not include carcinomatous meningitis which is excluded regardless of clinical stability.
- Has active autoimmune disease that has required systemic treatment in the past 2 years (i.e. with use of disease modifying agents, corticosteroids or immunosuppressive drugs). Replacement therapy (e.g., thyroxine, insulin, or physiologic corticosteroid replacement therapy for adrenal or pituitary insufficiency, etc.) is not considered a form of systemic treatment.

CUPem	C/37/2017	Imperial College London	V7.0; 08.12.2021
-------	-----------	----------------------------	------------------

10. Has a history of (non-infectious) pneumonitis/interstitial lung disease that required steroids or has current pneumonitis/interstitial lung disease.
11. Has an active infection requiring systemic therapy.
12. Has a history or current evidence of any condition, therapy, or laboratory abnormality that might confound the results of the trial, interfere with the subject's participation for the full duration of the trial, or is not in the best interest of the subject to participate, in the opinion of the treating investigator.
13. Has known psychiatric or substance abuse disorders that would interfere with cooperation with the requirements of the trial.
14. Is pregnant or breastfeeding, or expecting to conceive or father children within the projected duration of the trial, starting with the pre-screening or screening visit through 120 days after the last dose of trial treatment.
15. Has received prior therapy with an anti-PD-1, anti-PD-L1, or anti-PD-L2 agent.
16. Has a known history of Human Immunodeficiency Virus (HIV) (HIV 1/2 antibodies).
17. Has known active Hepatitis B (e.g., HBsAg reactive) or Hepatitis C (e.g., HCV RNA [qualitative] is detected).
18. Has received a live vaccine or live-attenuated vaccine within 30 days of planned start of study therapy.

*Note: Seasonal influenza vaccines for injection are generally inactivated flu vaccines and are allowed; however intranasal influenza vaccines (e.g., Flu-Mist®) are live attenuated vaccines, and are not allowed.*

CUPem	C/37/2017	Imperial College London	V7.0; 08.12.2021
-------	-----------	----------------------------	------------------

## **5 PROCEDURES AND MEASUREMENTS**

### **5.1 Identification and recruitment of patients**

Potential patients will be identified either by their direct care team at a participating investigational site (i.e. principal and/or co-investigator), or as the result of referral to the principal and/or co-investigator by another doctor based within or outside of that investigational site. Recruitment will take place as part of routine hospital outpatient clinic visits at participating investigational sites.

### **5.2 Study Screening Assessments**

Written informed consent will be obtained before the patient undergoes any study specific procedures. Consent must be documented by the subject's dated signature or by the subject's legally acceptable representative's dated signature on a consent form along with the dated signature of the person conducting the consent discussion.

A copy of the signed and dated consent form should be given to the subject before participation in the trial.

Each patient will undergo screening during the 28 days prior to admission to confirm eligibility, as per Table 3. Tumour assessments and other clinical data obtained as standard of care prior to consent may be used for the study provided they comply with the protocol specified timelines.

Once consent has been obtained the patient should be added to the InForm Electronic Case Report Form (eCRF), where a unique Screening ID will be allocated, which should be used in all correspondence during the screening period.

A complete record of all patients who enter screening for the study, and also those who go on to be enrolled, must be maintained at each site. The local investigator is responsible for ensuring that this record includes the allocated trial ID as well as the patient identifiable data including name, hospital number and date of birth.

Eligible patients who take part in the study must meet all of the listed inclusion criteria and none of the exclusion criteria.

### **5.3 Treatment Period**

Patients will receive their study treatment until disease progression, unacceptable toxicity or withdrawal. Patients will be required to attend clinic for assessments to be performed during treatment as per Table of Assessments (Table 3).

### **5.4 End of Study Treatment Visit**

The mandatory Safety Follow-Up Visit should be conducted approximately 30 days after the last dose of trial treatment or before the initiation of a new anti-cancer treatment, whichever comes first. Subjects who are eligible for retreatment with pembrolizumab (Section 5.6) may have up to two safety follow-up visits, one after the Treatment Period and one after the Second Course Phase.

CUPem	C/37/2017	Imperial College London	V7.0; 08.12.2021
-------	-----------	----------------------------	------------------

## 5.5 Follow Up Visits

Subjects who discontinue trial treatment for a reason other than disease progression will move into the Follow-Up Phase and should be assessed every 8 weeks ( $\pm$  7 days) clinically and before / by radiological imaging 12 weekly by radiologic imaging to monitor disease status. Every effort should be made to collect information regarding disease status until the start of new anti-neoplastic therapy, disease progression, death, end of the study or if the subject begins retreatment with pembrolizumab (see Section 5.6). Information regarding post-study anti-neoplastic treatment will be collected if new treatment is initiated.

Subjects who are eligible to receive retreatment with pembrolizumab according to the criteria in Section 5.6 will move from the follow-up phase to the Second Course Phase when they experience disease progression.

### 5.5.1 Survival Follow-up

Once a subject experiences confirmed disease progression or starts a new anti-cancer therapy, the subject moves into the survival follow-up phase and should be contacted by telephone every 12 weeks to assess for survival status until death, withdrawal of consent, or the end of the study, whichever occurs first.

## 5.6 Second Course Phase (Retreatment Period)

Subjects who stop pembrolizumab with Stable Disease (SD) or better may be eligible for up to one year of additional pembrolizumab therapy if they progress after stopping study treatment. This retreatment is termed the Second Course Phase of this study and is only available if the study remains open and the subject meets the following conditions:

- **Either**
  - Stopped initial treatment with pembrolizumab after attaining an investigator-determined confirmed Complete Response (CR) according to RECIST 1.1, and
    - Was treated for at least 24 weeks with pembrolizumab before discontinuing therapy
    - Received at least two treatments with pembrolizumab beyond the date when the initial CR was declared
      - **OR**
  - Had SD, Partial Response (PR) or CR and stopped pembrolizumab treatment after 24 months of study therapy for reasons other than disease progression or intolerability

### AND

- Experienced an investigator-determined confirmed radiographic disease progression after stopping their initial treatment with pembrolizumab
- Did not receive any anti-cancer treatment since the last dose of pembrolizumab
- Has a performance status of 0 or 2 on the ECOG Performance Scale
- Demonstrates adequate organ function as detailed in Section 4.2
- Female subject of childbearing potential should have a negative serum or urine pregnancy test within 72 hours prior to receiving retreatment with study medication.
- Female subject of childbearing potential should be willing to use 2 methods of birth control or be surgically sterile, or abstain from heterosexual activity for the course of the study through 120 days after the last dose of study medication (Section

CUPem	C/37/2017	Imperial College London	V7.0; 08.12.2021
-------	-----------	----------------------------	------------------

6.10.2). Subjects of child bearing potential are those who have not been surgically sterilized or have been free from menses for > 1 year.

- Male subject should agree to use an adequate method of contraception starting with the first dose of study therapy through 120 days after the last dose of study therapy.
- Does not have a history or current evidence of any condition, therapy, or laboratory abnormality that might interfere with the subject's participation for the full duration of the trial or is not in the best interest of the subject to participate, in the opinion of the treating investigator.

Subjects who restart treatment will be retreated at the same dose and dose interval as when they last received pembrolizumab. Treatment will be administered for up to one additional year.

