## **TRIAL SUMMARY**

Abbreviated Title	CUPem
Clinical Indication	A Phase II, Two-Stage, Trial of Pembrolizumab in Cancer of unknown primary
Trial Type	Single Arm, non-randomised; Two-stage; Hypothesis generating
Type of control	None
Route of administration	IV
Trial Blinding	N/A
Treatment Groups	
The study initially opened with a two-cohort design:
 
(i) First Cohort: One or more lines of prior therapy
 
(ii) Second Cohort: First Line untreated CUP patients
 
A substantial amendment in February 2022 has formally closed the second cohort, due to the significant challenges in recruitment caused by the ongoing COVID-19 pandemic as well as associated clinical factors.

Number of trial subjects	Following the closure of the second cohort, the first cohort sample size has been expanded to 31-67 patients. Recruitment will end once 67 patients have been recruited into cohort 1 or at the end of December 2022, whichever is sooner. The precise statistical implications of the eventual recruitment total are detailed (section 8).
Eligibility Criteria	
The Eligibility Criteria are the same as used in the CUP-ONE trial in the UK, please see below.
 
 
• Histologically confirmation of a diagnosis of CUP, with imaging and all diagnostic investigations confirmed as CUP within a CUP MDT.
 
• ECOG Performance Status 0-2
 
• Patients must have disease that is not amenable to potentially curative options such as resection or radical radiotherapy
 
• If patient's disease presentation precludes tumour biopsy (inaccessible or biopsy thought not to be in the patient's best interest), the patient is not study eligible.
 

Estimated recruitment period	2 years
Estimated duration of trial	3.9 years including set up, recruitment, follow up and close down.
Duration of Participation	6-8 months

CUPem	C/37/2017	Imperial College London	V7.0; 08.12.2021
-------	-----------	----------------------------	------------------

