### 4.2 Inclusion Criteria

Patients who meet all of the following inclusion criteria will be considered eligible for this study:

1. Be willing and able to provide written informed consent/assent for the trial.
2. Be  $\geq 18$  years of age on day of signing informed consent.
3. Have measurable disease based on RECIST 1.1.
4. Be willing to provide consent for archival tumour (in the form of formalin fixed paraffin embedded (FFPE) block) or fresh tumour material (if judged technically feasible by radiologist) is mandatory for diagnosis and biomarker analysis.
5. Have a performance status of 0-2 on the ECOG Performance Scale.
6. Have had at least one prior line / regimen of chemotherapy appropriate for CUP (at least 2 cycles). Either did not have a RECIST response to first-line chemotherapy or progressing after an initial response, or are treatment intolerant to first-line chemotherapy due to unacceptable toxicity.
7. Adequate organ and bone marrow function (all screening tests should be performed within 10 days of treatment initiation):
  - a. Absolute neutrophil count (ANC)  $\geq 1.5 \times 10^9/L$
  - b. Platelets  $\geq 100 \times 10^9/L$
  - c. Haemoglobin  $\geq 9$  g/dL ( $\geq 90$  g/L) without transfusion or EPO dependency (within 7 days of assessment)
  - d. Serum creatinine  $\leq 1.5 \times$  Upper Limit of Normal (ULN) or Creatinine clearance\*  $\geq 60$  mL/min for patients with creatinine levels  $> 1.5 \times$  ULN  
\* Creatinine clearance should be calculated per institutional standard
  - e. Serum total bilirubin  $\leq 1.5 \times$  ULN or direct bilirubin  $\leq$  ULN for patients with total bilirubin levels  $> 1.5$  ULN
  - f. Aspartate aminotransferase [AST]  $\leq 2.5 \times$  ULN ( $< 5 \times$  ULN if liver metastases are present)
  - g. Alanine aminotransferase [ALT]  $\leq 2.5 \times$  ULN ( $< 5 \times$  ULN if liver metastases are present)
  - h. Albumin  $\geq 2.5$ g/dL
  - i. International Normalized Ratio (INR) or Prothrombin Time (PT)  $\leq 1.5 \times$  ULN (unless subject is receiving anticoagulant therapy as long as PT or PTT is within therapeutic range of intended use of anticoagulants)
  - j. Activated Partial Thromboplastin Time (APTT)  $\leq 1.5 \times$  ULN (unless subject is receiving anticoagulant therapy as long as PT or PTT is within therapeutic range of intended use of anticoagulants).

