**Table 4: ECOG Performance Status**

0	Fully active, able to carry on all pre-disease activities without restriction
1	Restricted in physically strenuous activity but ambulatory and able to carry out work of a light or sedentary nature. For example, light housework, office work
2	Ambulatory and capable of all self-care but unable to carry out any work activities. Up and about more than 50% of waking hours
3	Capable of only limited self-care, confined to bed or chair 50% or more of waking hours
4	Completely disabled. Cannot carry on any self-care. Totally confined to bed or chair

CUPem	C/37/2017	Imperial College London	V7.0, 08.12.2021
-------	-----------	----------------------------	------------------

5	Death
---	-------

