#### **6.9.6 PERMANENT DISCONTINUATION OF STUDY TREATMENT**

Patients may discontinue study medication for the following reasons:

- Confirmed radiographic disease progression
- Unacceptable adverse experiences as described in Table 2
- Intercurrent illness that prevents further administration of treatment
- Investigator's decision to withdraw the subject
- The subject has a confirmed positive serum pregnancy test
- Non-compliance with trial treatment or procedure requirements
- Completed 24 months of uninterrupted treatment with pembrolizumab or 35 administrations of study medication, whichever is later
- Confirmed complete response (CR) and treated for at least 24 weeks with pembrolizumab and had at least two treatments with pembrolizumab beyond the date when the initial CR was declared.

A subject may be granted an exception to continue on treatment with confirmed radiographic progression if clinically stable or clinically improved.

24 months of study medication is calculated from the date of first dose. Subjects who stop pembrolizumab after 24 months may be eligible for up to one year of additional study treatment if they progress after stopping study treatment provided they meet the requirements detailed in Section 5.6.

Date of permanent discontinuation and the reason will be recorded.

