#### **6.9.9 Discontinuation of Study Therapy after Complete Response**

Discontinuation of treatment may be considered for subjects who have attained a confirmed CR that have been treated for at least 24 weeks with pembrolizumab and had at least two treatments with pembrolizumab beyond the date when the initial CR was declared. Subjects who then experience radiographic disease progression may be eligible for up to one year of additional treatment with pembrolizumab via the Second Course Phase at the discretion of the investigator if no cancer treatment was administered since the last dose of pembrolizumab, the subject meets the safety parameters listed in the Inclusion/Exclusion criteria, and the trial is open. Subjects will resume therapy at the same dose and schedule at the time of initial discontinuation. Additional details are provided in Section 5.6.

CUPem	C/37/2017	Imperial College London	V7.0, 08.12.2021
-------	-----------	----------------------------	------------------

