#### **9.7 Non-Compliance and Serious Breaches**

All protocol deviations and protocol violations will be reported via the eCRF and reviewed by the Chief Investigator and reported to the JRO on a monthly basis.

An assessment of whether the protocol deviation/violation constitutes a serious breach will be made.

A serious breach is defined as a breach of the conditions and principles of GCP in connection with a trial or the trial protocol, which is likely to affect to a significant degree:

- The safety or physical or mental integrity of the UK trial subjects; or
- The overall scientific value of the trial.

The Sponsor will be notified within 24 hours of identifying a likely Serious Breach. If a decision is made that the incident constitutes a Serious Breach, this will be reported to the MHRA, UK REC and other participating countries within 7 days of becoming aware of the serious breach.

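### Protocol 5.6 makes ECOG 0 or 2 a condition for retreatment, so read literally it refuses PS 1 patients while admitting the less fit PS 2; entry is PS 0-2 throughout

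*Protocol*

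**What the plan says.** Section 5.6 opens the Second Course Phase only while the study remains open and only to patients who meet a list of conditions. The list begins with two alternative routes: stopping after a confirmed complete response, or stopping after 24 months with stable disease or better. Under the joining word AND come conditions that apply to both routes, among them "Has a performance status of 0 or 2 on the ECOG Performance Scale". Retreatment then lasts up to one additional year.

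Entry is described differently. The Trial Summary has "ECOG Performance Status 0-2". Inclusion criterion 5 in Protocol 4.2 has "Have a performance status of 0-2 on the ECOG Performance Scale", and SAP 3.4 repeats that criterion. The descriptions of the closed Cohort 2 in Section 3.1 of both documents also give PS 0-2.

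Table 4 of the protocol defines PS 1 as "Restricted in physically strenuous activity but ambulatory and able to carry out work of a light or sedentary nature" and PS 2 as "Ambulatory and capable of all self-care but unable to carry out any work activities".

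Three other sections deal with retreatment:
- Section 6.9.6, footnote 2, allows it after 24 months "provided they meet the requirements detailed in Section 5.6".
- Section 6.9.8 covers complete responders and 24-month completers in one sentence and refers both to the Section 5.6 criteria.
- Section 6.9.9, on complete responders, requires that "the subject meets the safety parameters listed in the Inclusion/Exclusion criteria" and closes by pointing to Section 5.6 for further detail.

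**The concern.** A performance-status criterion normally sets a ceiling: everyone at or below a given grade qualifies. A rule that admits 0 and 2 but skips 1 is not a ceiling. A patient who entered at PS 1, benefited, stopped as the protocol allows and progressed while still at PS 1 would fail the condition. The same patient would pass it after deteriorating to PS 2.

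What is at stake is treatment access under an eligibility rule. A site applying the text as written would withhold up to a year of drug from a PS 1 patient who met everything else, in a setting where the protocol says (Sections 1.3.1 and 8.2) that no standard of care exists. A site that used common sense and retreated would be outside the protocol, and Section 9.7 says that "All protocol deviations and protocol violations will be reported via the eCRF".

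**Working it through.** No sample-size or power figure is involved, so the check is a comparison of the eligibility statements.

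**Step 1: the sets as written.**

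| Place | PS grades admitted |
|---|---|
| Trial Summary (entry) | {0, 1, 2} |
| Protocol 4.2, item 5 (entry) | {0, 1, 2} |
| SAP 3.4, item 5 (entry) | {0, 1, 2} |
| Protocol 3.1 and SAP 3.1 (closed Cohort 2) | {0, 1, 2} |
| Protocol 5.6 (retreatment) | {0, 2} |

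The entry set minus the retreatment set is {1}. The two rules differ in the middle grade only.

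**Step 2: is {0, 2} a coherent fitness rule?** Table 4 orders the grades: PS 1 patients can still do light or sedentary work, PS 2 patients can do none. A ceiling at 0 gives {0}, at 1 gives {0, 1}, and at 2 gives {0, 1, 2}. No ceiling gives {0, 2}.

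**Step 3: which wording could have been meant?** The two plausible candidates are 0-2, matching entry, and 0-1, a deliberate tightening. PS 1 belongs to both. The protocol's stated interest in PS 2 patients (secondary objective and hypothesis, Section 2.2) and the uniform entry range favour 0-2, but nothing in the documents settles the upper limit.

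**Step 4: does another section override the line?**
- 24-month route: Section 6.9.6, footnote 2, refers to Section 5.6, and Section 6.9.8 does the same.
- Complete-response route: Section 6.9.8 refers to Section 5.6. Section 6.9.9 adds the safety parameters from the inclusion and exclusion criteria, then refers to Section 5.6.

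Both routes therefore pass through the 0-or-2 condition. If the safety parameters in Section 6.9.9 were taken to include ECOG status, that would bring in {0, 1, 2} as a further requirement. A patient must satisfy both, and {0, 1, 2} ∩ {0, 2} = {0, 2}, so PS 1 is still refused.

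**Step 5: what in the analysis depends on the line?** Retreatment starts only after progression. PFS as defined in SAP 5.1 ends at first evidence of progression, so it has already been determined. The sample-size calculations in Protocol 8.2 and SAP 3.5 do not use retreatment. Survival after progression and drug exposure could change in the few patients concerned, by an amount the documents do not allow anyone to estimate. The SAP does not repeat the retreatment criteria.

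**The case against.** The best case against giving this much weight is that it is a slip of a word or a dash in a conditional clause. Few of the 31-67 patients can reach the phase, a sensible investigator would probably read the line as 0-2, and nothing shows that any PS 1 patient has been or will be turned away. All of that is fair, and it limits the size of the point. It does not remove it, because an eligibility condition should not depend on the reader correcting it, and a site that does correct it must report a deviation.

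Two stronger readings are tempting and should be resisted.

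- A reader might infer from Section 6.9.9 that complete responders fall under a different ECOG rule from 24-month completers, so that sites face two conflicting rules. The documents do not support this. Section 6.9.8 sends both groups to Section 5.6, Section 6.9.9 itself points there, and any ECOG requirement it brings in adds to Section 5.6 without displacing it.
- A reader might try to work out from the recruitment and closure dates exactly who could still reach retreatment. Such dates are best cases only. Section 6.9.6 sets planned completion at 24 months or 35 administrations, whichever is later, and Section 5.8 allows treatment intervals to be lengthened by 1 to 2 weeks during the pandemic. The documents give neither a complete-response rate nor a performance-status mix, so no count follows.

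**Conclusion.** The point holds. As written, Section 5.6 is a wrong treatment-access rule: on both retreatment routes it excludes PS 1, the fitter grade, and admits PS 2, with no justification and against a uniform entry range of 0-2. It is almost certainly a drafting error, but it is operative text in version 7.0 and no other section corrects it.

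The size is small. It concerns a few patients, and their number cannot be computed. PFS, sample size and power are unaffected. It would go too far to call this a threat to the trial's efficacy conclusions, or to say that patients have been wrongly refused; the documents show neither. The conclusion rests on the literal wording of the line and on the Section 5.6 list being mandatory, as its introduction states. That 0-2 was the intended range is the better-supported reading but is not established.

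**What to change.** In Section 5.6, replace the ECOG condition with a performance status of 0-2. The clinical team should confirm the upper limit; if they want a tighter rule the alternative is 0-1, and PS 1 is admitted in either case. No change to Section 6.9.9 is needed, since it already refers to Section 5.6, and the SAP needs none.

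The cost is a one-line wording amendment: classification by the Trial Management Group and review by the Protocol Development Group (Section 9.3.2), plus the usual approvals (Sections 9.3.2, 9.4 and 9.5). ECOG status is already recorded at Follow Up visits (Table 3), so no new data are needed, and the sample size and analysis stay as they are.
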